10.2.4 Follow-up Period

Follow-up contact (10 to 14 days after last dose of study drug)

All subjects will be contacted via telephone (or in-person if still in the hospital) within 10 to 14 days after the last dose of study medication for follow-up that will include:

- Record concomitant medications
- Monitor AEs
- Review of data for hepatobiliary AEs
- Monitor prespecified postoperative complications
- Determine whether hospital readmission occurred and reason for readmission

A certified letter will be sent to any subject not contacted after 3 attempts by telephone.

Follow-up visit (30 days + 15 days after hospital discharge)

All subjects are to return for a follow-up visit 30 days (+ 15 days). Procedures to be conducted at this visit include:

- Perform physical examination, including weight. Any clinically relevant physical abnormalities (with the exception of surgical scars) that were not present at screening should be recorded as AEs.
- Record vital signs (blood pressure, heart rate, respiratory rate, and temperature)
- Record concomitant medications
- Monitor AEs
- Monitor prespecified postoperative complications
- Determine whether hospital readmission occurred and reason for readmission
- If elevated at discharge and trending down, then liver tests will be completed at the 30-day follow-up visit. If a subject remains in the hospital for an AE of elevated tests, then levels will be followed until resolution.

If a patient does not return for a scheduled visit, all necessary measures should be taken to contact the patient and document the patient's outcome.

Reasonable efforts should be made to contact subjects who are lost to follow-up. A certified letter will be sent to any subject not contacted after 3 attempts by telephone. These efforts must be documented in the subject's file.

Exceptional measure for COVID-19

Depending on the COVID-19 situation (and/or to reduce burden of patient travel as needed), measures below may be considered for the 30-day follow-up visit.

- Window for the 30 day follow-up can be extended to +15 days after hospital discharge.
- If subject is unable to come to clinic for in-person visit, then performing LFT laboratory tests (if needed) at a local hospital, or regional independent laboratory located near the subject will be considered. Local laboratory results should be documented in subject's file.

- Telephone conversation or video conferencing may be used for other procedures at this visit. Additionally, local at-home services performed by trained non-study personnel may be used for measurement of vital signs and physical examinations.

11 EFFICACY ASSESSMENTS

The Schedule of Assessments (Table 1) outlines the efficacy assessments to be performed throughout the study and their timing.

11.1 Surgery Data Collection

During the surgery, the following information should be collected and recorded on the eCRF:

- Surgery start and stop times (stop time is defined as the time of the last stitch or staple)
- Any estimated blood loss
- Need for blood transfusion
- Total intraoperative IV fluid type and volume
- NGT removal time, if used

11.2 Gastrointestinal Assessments

Gastrointestinal assessments will be performed twice daily in the morning and afternoon, starting on randomization Day 1, and continuing until hospital discharge or study termination.

Assessments must be separated by at least 6 hours. Gastrointestinal assessments will include:

- Recording time of first:
 - Clear liquid toleration (i.e., time at which the subject transitions from clear liquids to the next diet stage [full liquids or solids])
 - Solid diet toleration (i.e., able to eat a meal that requires chewing without a vomiting episode by the time the next consecutive meal is offered)
 - Note, if the first solid meal is consumed on the day of hospitalization (i.e., the day of surgery), the time to toleration of solids is as stated (e.g., the time to eat solids without a vomiting episode by the time the next consecutive meal is offered). Further, if the first solid meal is consumed on the day of discharge, the time to toleration of solids criteria is met if there is no vomiting prior to discharge. In all cases, the actual time that should be recorded on the eCRF is the time the meal was consumed by the subject, not the cutoff time for vomiting prior to next consecutive meal or discharge.
 - Absence of distention + presence of bowel sounds + flatus (time of when all 3 conditions have been achieved)
- Record time subject is ready for hospital discharge (based solely upon recovery of GI function as determined by the treating medical team)

11.3 Electronic Diary Assessments

Subjects will record in their eDiaries on all postoperative in-hospital days. They should record the following:

- First flatus (record in real time)
- First BM (record in real time)

- Nausea occurrence and bothersomeness (a 24-hour reflection)
- Vomiting/retching occurrence/number of episodes (a 24-hour reflection)
- Abdominal bloating occurrence and bothersomeness (a 24-hour reflection)

The investigator will assess eDiary entries at study visits starting on Randomization Day 1 and continuing daily until hospital discharge or study termination.

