6.2 Study Endpoints

6.2.1 Primary Efficacy Endpoint

Primary endpoint: The primary efficacy endpoint is the time to achieve recovery of GI motility as measured by a composite endpoint representing upper (time to first toleration of clear liquids) AND lower (time to first BM OR absence of distention AND presence of bowel sounds AND flatus) GI recovery. This endpoint is referred to as gastrointestinal recovery (GIR).

GIR=Time to first toleration of clear liquids (i.e., time at which the subject transitions from clear liquids to the next diet stage; [full liquids or solids])
AND
(Time to first BM) OR (absence of distension + presence of bowel sounds + flatus)

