6.2.2 Secondary Efficacy Endpoints

The secondary efficacy endpoints are as follows:

- Time to GI-2 recovery (i.e., time to first toleration of solids AND time to first BM)
- Time to ready for discharge (based solely on GI recovery)
- Time to discharge order written
- Length of hospital stay (based on calendar day of discharge order written)
- Proportion of GIR responders
 - GIR by day
- POI-related morbidity (primary POI only)
 - POI that required readmission within 7 days of discharge, or

- Need for postoperative NGT insertion to manage symptoms of POI (i.e., vomiting/retching, abdominal distension) per protocol guidelines
- Time to first toleration of clear liquids, i.e., time at which the subject transitions from clear liquids to the next diet stage (full liquids or solids)
- Time to first BM
- Time to absence of distension and presence of bowel sounds and flatus (i.e., time to when all 3 conditions have been achieved)
- Time to toleration of solids (i.e., able to eat a meal that requires chewing without a vomiting episode by the time the next consecutive meal is offered).
 - Note, if the first solid meal is consumed on the day of hospitalization (i.e., the day of surgery), the time to toleration of solids is as stated (e.g., the time to eat solids without a vomiting episode by the time the next consecutive meal is offered). Further, if the first solid meal is consumed on the day of discharge, the time to toleration of solids criteria is met if there is no vomiting prior to discharge. In all cases, the actual time that should be recorded on the eCRF is the time the meal was consumed by the subject, not the cutoff time for vomiting prior to next consecutive meal or discharge.

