8.1 Inclusion Criteria

To be considered eligible to participate in this study, a subject must meet all the inclusion criteria listed below:

1. Male or female \geq 18 years of age
2. Women of childbearing potential (WOCBP) or men whose sexual partners are WOCBP; must be able and willing to use at least 1 highly effective method of contraception during the study and for 30 days after the last dose of study drug. A female subject is considered to be a WOCBP following menarche and until she is in a postmenopausal state for 12 months or otherwise permanently sterile (for which acceptable methods include hysterectomy, bilateral salpingectomy, and bilateral oophorectomy). Highly effective methods of contraception include intrauterine contraceptive device; intrauterine hormone-releasing system; combined hormonal or progestogen-only contraception associated with inhibition of ovulation (oral, intravaginal, or transdermal); bilateral tubal ligation or occlusion; vasectomy; condom in combination with contraceptive cream, jelly, or foam; or abstinence. Male subjects must agree to not donate sperm during the study period after drug is given until the 30-day follow-up.
3. American Society of Anesthesiologists Physical Status Score of 1 to 3
4. Scheduled for an elective BR as listed below via open or laparoscopic (straight, hand-assisted, robotically assisted) approach
 - a) Small BR
 - b) Large BR (partial colectomy)
 - c) Total colectomy with ileo-rectal anastomosis
 - d) Rectal resection (low anterior resection)
5. Based on investigator assessment, subject's hospital stays anticipated to be \geq 4 calendar days (i.e., at least 3 overnight stays). It is anticipated that the subject will not be discharged until they have achieved upper and lower GI recovery per the protocol definition.
6. Eastern Cooperative Oncology Group performance status of 0 or 1
7. Ability to understand the study procedures, have agreed to participate in the study program, and have voluntarily provided informed consent

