14.2 Determination of Sample Size

The study is expected to enroll approximately 402 eligible subjects (with expected loss to follow-up or censorship of primary endpoint) with 1:1:1 randomization ratio over a post-surgery period (up to 10 days). The study is sized to achieve approximately 87% power to detect a hazard ratio (HR; TU-100 versus placebo) of 1.428 for GIR, which translates into an improvement in median time to GIR from 48 hours (2.0 days) for placebo (reference) to 34 hours (1.4 days) for TU-100 at a 0.05 significance level of one-sided log-ranked test for equality of time to GIR survival curve.

Based on historical evidence, it is assumed that a small proportion of subjects will be lost to follow-up or will have events censored due to required analytical methods. To account for this anticipated loss in contribution of events to the primary endpoint, an additional 36 subjects (approximately 10% of 366) will be enrolled to achieve a final sample size of 402 subjects (134 per group).

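### Subjects discharged before a first bowel movement are right-censored for GI-2 recovery and time to first BM, and no later contact collects the missing time

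*Combined protocol and SAP*

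**What the plan says.** **Endpoints that need a BM.** Section 6.2.2 lists "Time to GI-2 recovery (i.e., time to first toleration of solids AND time to first BM" and, separately, time to first BM.

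**Recovery and discharge that do not.** Section 6.2.1 defines the lower-GI part of GIR as "Time to first BM) OR (absence of distension + presence of bowel sounds + flatus". Inclusion criterion 5 (Section 8.1) says "It is anticipated that the subject will not be discharged until they have achieved upper and lower GI recovery per the protocol definition". Section 11.2 leaves readiness for discharge to the treating team's view of GI function. No section requires a BM before discharge.

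**When BM is recorded.** First BM is an eDiary item, and Section 11.3 says "Subjects will record in their eDiaries on all postoperative in-hospital days". Section 10.2.3 repeats this and includes the discharge day. The site's twice-daily GI assessments run from Day 1, "continuing until hospital discharge or study termination" (Section 11.2). The times they list are clear liquids, solids and the three-sign combination, not first BM.

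**After discharge.** The 10–14 day contact and the 30-day visit (Section 10.2.4) cover medications, adverse events, complications and readmission ("Determine whether hospital readmission occurred and reason for readmission"). The visit adds an examination, vital signs and, if needed, liver tests. Neither asks for a first BM.

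**Censoring.** Section 14.5.2 censors TGIR at 240 hours and leaves the rules for secondary time-to-event endpoints to the SAP. The text available for this review contains no such rule.

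**The concern.** Observation of first BM stops at a time set by a different recovery route. A subject who is eating, passing flatus and not distended can satisfy the protocol's recovery definition, go home and have a first BM the next day. That time is collected nowhere.

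Two things are at stake. First, each such subject is a lost event for GI-2 and for time to first BM. Second, Section 14.5.3 applies the primary-endpoint methods (Cox model, log-rank test, Kaplan-Meier estimates, restricted mean) to these endpoints. In their standard form these methods assume that censoring is independent of the event time. Here subjects are censored because they are recovering, and a drug that speeds diet or flatus would change who is censored.

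The endpoint is not incidental. Sections 5.3 and 5.4 cite faster first BM in some patients as the signal from the Japanese trials.

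**Working it through.** **1. The text, step by step.** GI-2 and time to first BM need a BM (6.2.2). GIR does not (6.2.1). The discharge expectation refers to the GIR-type definition (8.1). BM recording ends at discharge (10.2.3, 11.3, Table 1). Follow-up does not ask for it (10.2.4). It follows that a subject discharged by the flatus route before a BM has a known BM-free time up to discharge and nothing after it.

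**2. The plan's own figure.** Section 14.2 claims "approximately 87% power to detect a hazard ratio (HR; TU-100 versus placebo) of 1.428 for GIR", one-sided 0.05, for an "improvement in median time to GIR from 48 hours (2.0 days) for placebo (reference) to 34 hours (1.4 days) for TU-100". Before the loss allowance there are 366 subjects, so 122 per arm and 244 per comparison with placebo. With 1:1 allocation and D events (Schoenfeld),

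power = Φ( ln(HR) × √(D/4) − 1.645 ).

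With HR = 1.428 and D = 244: 0.3563 × 7.810 − 1.645 = 1.138, and Φ(1.138) = 87.2%. The stated 87% is reproduced, with every one of the 244 counted as an event. It applies to GIR. The plan gives no power or event count for GI-2 or first BM.

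**3. Lost events.** As an illustration, give first BM the same hazard ratio and the same 244 subjects, and let a share f, equal in both arms, leave without a BM. Then D = 244 × (1 − f).

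| Assumed f | Events | Power |
|---|---|---|
| 0% | 244 | 87.2% |
| 5% | 232 | 85.7% |
| 10% | 220 | 84.1% |
| 20% | 195 | 80.0% |
| 30% | 171 | 75.3% |
| 40% | 146 | 69.4% |

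**4. Informative censoring.** Two simulations were run, with inputs that are assumptions and not taken from the plan.

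*Simulation A.* Exponential times; placebo median 60 h for BM and 48 h for the flatus route; correlation parameter 0 or 0.5; discharge 24 h after whichever lower-GI event comes first, not before 72 h and not after 240 h. The hazard ratio is the ratio of events per person-hour.

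| True effect of TU-100 | Censored, placebo | Censored, TU-100 | Observed BM HR |
|---|---|---|---|
| None | 31–34% | 31–34% | 1.00 |
| Flatus route only (1.428) | 31–34% | 36–38% | 0.995–1.003 |
| Both routes (1.428) | 31–34% | 22–26% | 1.42–1.47 |

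*Simulation B.* Lognormal times; placebo medians 30 h (diet), 42 h (flatus and examination) and 48–72 h (BM); correlation 0.3–0.6; TU-100 multiplies diet and flatus times by 34/48; discharge 6–42 h after GIR and not before about 66 h. The spread of the times is also assumed.

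- About 10–55% of an arm is censored before a BM.
- With no BM effect, the observed HR is about 0.94–1.00.
- When BM time is also cut by 20%, the observed HR is, for example, about 1.42–1.51 against a true 1.40.
- The Kaplan-Meier 25th percentile is unbiased, and the median is off by at most about 6 h.
- The error in the 75th percentile runs from under an hour to tens of hours. The large errors occur only when BM is late and TU-100 does not affect it. If TU-100 also speeds BM, fewer TU-100 subjects are censored and their 75th-percentile error is the smaller one.

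**The case against.** The case for leaving the plan alone has several parts.

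- **Size.** The share leaving without a BM is undocumented, and the plan points towards a small one. Stays of at least three nights are anticipated (8.1), and Section 7.2 says patients are not routinely sent home before GI milestones. This stands as a limit on any number given here. It does not close the gap, because neither section makes a BM one of the milestones.
- **The SAP.** It may set a censoring rule and sensitivity analyses for informative censoring, and the absence of a rule from the text reviewed does not show that none exists. That also stands. A rule can say how to treat a missing time; it cannot supply one that was not collected.
- **Scope.** The trial targets in-hospital outcomes and dosing stops at discharge. A BM at home is off drug, outside the ERAS setting and recalled. This is a fair argument for flagging such times and keeping the discharge-censored analysis alongside.
- **Importance.** The BM signal comes from Japanese trials with different care and dosing, as Section 5.3 cautions. P values are nominal, and the order of the secondary list confers no priority.

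Stronger readings are tempting, and the documents do not support them. A reader might infer that the two endpoints are simply unobserved in these subjects; in fact the subjects stay in the analysis as right-censored. A reader might infer that GIR is compromised; it is not, because these subjects reached it by the flatus route. A reader might also infer a raised false-positive risk, or quartiles that systematically disfavour TU-100. In the simulations the null hazard ratio stays at or slightly below 1, and the quartile error changes direction with the assumptions.

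**Conclusion.** The gap is real and can be read directly from the text. It concerns two secondary endpoints only. The firm consequence is lost events: with an assumed 5–40% leaving before a BM, 232 down to 146 events per comparison in place of 244, and 86% down to 69% power at a hazard ratio of 1.428. That calculation borrows the GIR effect size and assumes equal loss in both arms.

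Bias is plausible because discharge follows recovery, but it is secondary. The hazard ratio stays near 1 (about 0.94–1.00) without a BM effect and is modestly exaggerated with one. Among the quartiles, only the 75th percentile can be badly off, and by an amount and in a direction that the documents cannot settle. This is a worthwhile, inexpensive improvement in data collection. It is not a threat to the primary analysis.

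**What to change.** At discharge, record whether a first BM has occurred. If not, ask the subject to note the date and time of the first BM at home, and collect it at the existing contact 10–14 days after the last dose. Dosing starts the day after surgery, so that contact falls at least 11 days after surgery, beyond the 240-hour limit, and one call is enough.

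Use the time for time to first BM and, where solids were tolerated before discharge, for GI-2, up to 240 hours. Censor at discharge only if the time cannot be obtained. Flag these times as recalled and off treatment, and report the analysis censored at discharge as a sensitivity analysis. State both rules in the SAP.

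The cost is one question at discharge, one at an existing contact and one eCRF field. No treatment or discharge rule changes. The downside is that recalled times are less exact and reflect a period off study drug. The change has to be made prospectively, because later analysis cannot recover times that were never asked for.

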11.4 Time to Writing of Discharge Order

The time when the discharge order is written should be noted on the eCRF by the investigator.

11.5 Time to Discontinuation of IV Fluids

The time of discontinuation of IV fluids and the transition to oral liquids should be noted on the eCRF by the investigator.

11.6 Time to Transition of Oral Analgesics

The time when the subject is able to transition from IV to oral analgesics should be noted on the eCRF by the investigator.

11.7 Prespecified Postoperative Complications

Any postoperative complications should be recorded on the eCRF by the investigators. These prespecified complications include:

- Need for blood transfusion information (recorded as part of in-surgery information)
- Readmission to hospital within 7 days and 30 days of discharge
- POI-related morbidity as evidenced by:
 - POI that required readmission within 7 days of discharge, or
 - Need for postoperative NGT insertion to manage symptoms of POI (i.e., vomiting/retching, abdominal distension) per protocol guidelines
- Other postoperative complications including:
 - Prolonged POI
 - Minimal incision BR (laparoscopic or robotically-assisted or hand-assisted): Unresolved POI by postoperative Day 3
 - Laparotomy (open) BR: Unresolved POI by postoperative Day 5

Note: POI = primary POI (i.e., POI that is not secondary to surgical complication, such as anastomotic leak, abscess formation, or sepsis)

- Recurrent POI (prolongs hospital stay or results in readmission – based on investigator assessment)
- Surgical site infection
- Anastomotic leak
- EPSBO

- Confirmed by the presence of a transition point between dilated and decompressed bowel demonstrated on abdominal imaging

12 SAFETY ASSESSMENTS

Safety assessments (vital signs, physical examinations, ECG recording, AEs, clinical laboratory results [routine hematology and biochemistry]) are to be performed at protocol-specified visits, as specified in the Schedule of Assessments ([Table 1](#)).

12.1 Medical History

Medical history will be recorded at screening. Investigators should document the occurrence, signs, and symptoms of the subject's ongoing pre-existing conditions present at the time when informed consent is given and up to the time of first dosing, significant surgeries (i.e., cardiac, vascular, or general thoracic surgery), and GI-related conditions/surgeries. Medical history will include alcohol consumption, illicit drug use, and smoking history, if applicable.

Illnesses first occurring or detected during the study and/or worsening of a concomitant illness during the study are to be documented as AEs on the eCRF in accordance with [Section 12.6](#). All changes not present at baseline or described in the past medical history and identified as clinically noteworthy must be recorded as AEs.

Additionally, demographic data will be collected for all subjects and include age at study entry, gender, race, ethnicity, weight, and height, according to applicable regulations.

12.2 Vital Signs

Vital signs (body temperature, respiratory rate, heart rate, and systolic and diastolic blood pressure measurements) will be evaluated at the visits indicated in the Schedule of Assessments ([Table 1](#)). All vital signs will be measured after the subject has been resting in a sitting position for at least 5 minutes. Blood pressure measurements are to be taken in the same arm for the duration of the study. Day 1 (Postoperative Day 1) vital signs should be taken before study drug administration.

Vital sign measurements will be repeated if clinically significant or machine/equipment errors occur. Out-of-range blood pressure, respiratory rate, or heart rate measurements will be repeated at the investigator's discretion. Any confirmed, clinically significant vital sign measurements must be recorded as AEs.

